#### **6. SPECIFIC AIMS**

##### **Aim 1: Develop the *LinkPositively* mobile intervention through focus groups (FGs) with Black WLHA affected by interpersonal violence, peer navigators, and service providers, and refine iterations through input from the San Diego CFAR Disparities Core CAB.**

Four FGs, with 6-8 HIV-positive Black WLHA reporting a lifetime history of interpersonal violence by an intimate partner (n=2 FGs) and non-intimate partner (n=2 FGs); one FG with 4-6 Peer Navigators employed at HIV clinics/service agencies; and 4-6 key informant interviews with service providers will be conducted in San Diego, CA. Group differences will be explored to optimize *LinkPositively* across different types of reported perpetrators. The outcomes will be feedback on proposed intervention components and suggestions for new features, as well as recommendations for how to address challenges to engagement with *LinkPositively*. Aim 1 will culminate in usability testing by Black WLHA affected by IPV (n=8), to finalize intervention components and procedures.

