## 7. BACKGROUND AND SIGNIFICANCE

### Background and Significance

**Black women are disproportionately affected by HIV and interpersonal violence.** Black women living with HIV/AIDS (WLHA) in the US are less likely to be engaged in HIV care and adherent to antiretroviral therapy (ART) compared to other racial/ethnic groups (1-3). Black WLHA account for 61% of diagnoses among women of all races and ethnicities (4), only 56% are retained in care (1), and 49% virally suppressed (1). Black WLHA are particularly affected in San Diego County, CA, with HIV prevalence rates 8 times higher than that observed for White WLHA (5) and are underserved and understudied. Blacks on ART in San Diego are less likely to be virally suppressed than Latinos or Whites (6). Concurrently, Black women are disproportionately affected by interpersonal violence, defined as ever experiencing physical (e.g., hit, slapped, choked), sexual (e.g., forced vaginal/anal sex), and/or psychological (e.g., yelled at, belittled, controlling behaviors) abuse by a male intimate partner (e.g., spouse, boyfriend, dating partner) or non-intimate partner (e.g., relative, friend, stranger). Interpersonal violence is comprised of commonly reported forms of violence (i.e., intimate partner violence (IPV), rape, contact sexual violence, childhood abuse). Whereas the national prevalence of lifetime IPV is 45% (7), Black women report 35% higher IPV than White women (8). Moreover, although national data estimates the lifetime prevalence of rape among Black women at 21% (7), community-based samples estimate prevalence rates of rape as high as 38-54% (9-12).

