### **Study Population:**

#### **AIM 1**

In Phase 1 (Aim 1), eligible participants for the focus groups and interviews will be: (1) Black WLHA (including transgender women) with a history of interpersonal violence (n=6-8 per FG; total of 4 FGs); (2) Black WLHA (including transgender women) with a history of interpersonal violence who act in a professional capacity as a Peer Navigator (n=4-6; one FG); and (3) Key Informants (n=4-6) will be leadership at local clinics and community-based organizations known to provide services to women in the areas of HIV/AIDS care and domestic violence services, such as UCSD Owen Clinic and Mental Health America. Phase 1 will culminate in usability testing, Beta Testing, by Black WLHA affected by interpersonal violence (n=8; 4 with histories of interpersonal violence perpetrated by a current or former intimate partner and 4 with histories of interpersonal violence perpetrated by a non-intimate partner [e.g., family member, friend, stranger]), to finalize intervention components and procedures.

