#### **AIM 2**

In Phase 2 (Aim 2), eligible participants for the RCT will self-report: (a) female gender (including transgender women), (b) Black or African American racial/ethnic background, (c) aged 18 years or older, (d) HIV-positive status, (e) ever experienced physical, sexual, and/or psychological abuse by a current or former partner or non-partner (e.g., relative, friend, stranger), (f) owner of a smartphone with internet browsing capabilities, and (g) English speaking. Purposive sampling will be used to ensure that groups are balanced with respect to type of perpetrator (current or former intimate partners [e.g., spouse, boyfriend, dating, casual] and non- intimate partners [e.g., family member, friend, stranger]) and retention in HIV medical care status (linked to care but have fallen out of care [i.e., no ART prescription filled, no viral load labs, or no HIV care visits with an ART-prescribing provider in the past year] versus linked to and retained in care [i.e., ART prescription filled, viral load labs, or HIV care visits with an ART prescribing provider in the past year]).

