contacted for follow-up assessments. Informed consent, completion enrollment paperwork, and assessments will occur in field offices in San Diego County (UC San Diego AntiViral Research Center, located at [name]), Los Angeles County (Charles R. Drew University of Medicine and Science, Clinical and Translational Science Institute, [name]), Alameda County (WORLD, located at [name]), Oklahoma City (Guiding Right Offices, [name], [name], and [name]) and Tulsa County (Guiding Right, Inc., [name]). Following the baseline visit, participants will be randomized using a randomization sequence at a 1:1 ratio into the intervention or control arm on a rolling basis.

**All Study Visits.** At all study visits (Baseline, Follow-Up 1, Follow-Up 2), participants will undergo an interviewer-administered quantitative survey and biological sample collection (hair). An increasing payment schedule will be used to enhance motivation to complete surveys. Specifically, women will receive \$25 for completing the baseline visit, \$30 for completing the 3-month follow-up visit, and \$40 for completing the 6-month follow-up visit, with a \$10 bonus for completing all 3 visits. Due to the ongoing COVID-19 pandemic, follow-up study visits may occur virtually, over the secure video conference platform Zoom. For all in-person study activities, participants and staff will be required to wear face masks and physically distance when feasible. If participants do not have access to a face mask, one will be provided to them upon entry to the private research office space. Additionally, all participants will be screened for symptoms of COVID-19 by the Research Associate one day in advance of all in-person study visits, and again upon arrival at the private research office space.

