**Quantitative Survey.** The quantitative survey will include the following sections: (1) Demographic questions (e.g. age, biological sex at birth, gender identity, race/ethnicity, education, sexual orientation, marital status, employment, number of children, housing status, medical insurance status, food insecurity); (2) Socioeconomic status; (3) Mental health and behavioral health history (e.g. depression, anxiety, alcohol and substance use diagnosis and/or abstinence, lifetime history of trauma); (4) HIV care and treatment history (e.g. obtaining medical care, usual source of medical care, treatments, medications, insurance status, barriers to HIV treatment, self-reported adherence, adherence self-efficacy); (5) Support and Coping (e.g. social support, coping self-efficacy, ancillary support utilization); (6) Health care interactions (e.g. HIV stigma, medical mistrust) (7) Syndemic factors (e.g. interpersonal violence). [See Quantitative Survey].

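### Purposive sampling is said to ensure balanced groups, but *groups* is undefined, neither reading is backed by strata or Aim 2 counts, and no estimate accounts for baseline care status

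*Combined protocol and SAP*

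**What the plan says.** The balance statement appears twice in the protocol in the same words, in section 9 (Study Population, Aim 2) and section 10 (Human Subjects, Aim 2): "Purposive sampling will be used to ensure that groups are balanced with respect to type of perpetrator" and retention in HIV care status. Neither place defines *groups*.

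Care status has two categories. The first is "linked to care but have fallen out of care", explained as "no ART prescription filled, no viral load labs, or no HIV care visits with an ART-prescribing provider in the past year". The second is linked to and retained in care, explained by the same three indicators in positive form, also joined by *or*.

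On allocation, section 9 (Baseline Study Visit) says "participants will be randomized using a randomization sequence at a 1:1 ratio into the intervention or control arm on a rolling basis". The Treatment Conditions paragraph adds that the biostatistician team generates the sequence. Neither mentions strata, blocks or minimization. Section 10 gives 40 women per arm.

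Aim 1 does give counts by perpetrator type: two focus groups for each type (section 6), and for beta testing "4 with histories of interpersonal violence perpetrated by a current or former intimate partner and 4 with histories of interpersonal violence" by a non-intimate partner (section 9). Aim 2 gives only the total of 80.

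The SAP (Intervention Impact) reports medians with interquartile ranges, or frequencies, by arm at baseline, 3 and 6 months, and compares trends. It gives no between-arm estimate and no adjustment.

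**The concern.** Sampling decides who enters a trial; allocation decides which arm they join. A sampling method cannot ensure that arms are alike, so under the arm reading the assurance has no stated mechanism behind it. Under the composition reading the statement is workable, but without a count per category nobody can check whether it was met.

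Care status matters most here. Retention in care and viral suppression are two of the three primary outcomes in section 6 (Aim 2), and whether a woman was in care at entry is likely to predict both. The pilot is meant to show preliminary impact ahead of a larger trial, so the size and direction of the arm differences will be read even without a test. As written, a reader cannot tell whether balance was built into allocation, sought in recruitment or left to chance.

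**Working it through.** The plan states no figure for balance, so there is none to reproduce; 80 women at 1:1 gives 40 per arm, as stated.

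**1. Chance imbalance if allocation is unstratified.** Let K of the 80 women have a given factor, and let k of them fall in the intervention arm. With a 40/40 split, k is hypergeometric (80, K, 40) and the arm gap is (2k − K)/40. K is assumed, because Aim 2 gives no counts.

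| Assumed prevalence | K | Mean absolute gap | P(gap ≥ 15 points) | P(gap ≥ 20 points) |
|---|---|---|---|---|
| 50% | 40 | 8.8 points | 26% | 12% |
| 30% | 24 | 8.1 points | 22% | 9% |
| 20% | 16 | 7.0 points | 16% | 5% |

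The 50% row is the case in which purposive sampling fills the sample perfectly, and its gaps are the largest.

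**2. Effect on a crude arm difference.** Shift = arm gap × difference in outcome rate between care-status categories. That difference is assumed to be 30 to 60 points.
- Mean gap: 7.0 × 0.30 = 2.1 points up to 8.8 × 0.60 = 5.3 points.
- A 15-point gap: 15 × 0.30 = 4.5 points up to 15 × 0.60 = 9.0 points.

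**3. Sampling error for comparison.** The 95% half-width is 1.96 × √(2p(1 − p)/n). For p, take the background rates of 49% (viral suppression) and 56% (retention) in section 7.
- n = 40 per arm: 21.9 and 21.8 points.
- n = 32 per arm (0.80 × 40, reading the 80% second-visit retention in section 9 as a share of those enrolled): 24.5 and 24.3 points.

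The shifts in step 2 are well inside these.

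**4. Gain from a stratified estimate.** Total variance is T = p(1 − p). Within-stratum variance is W = T − π(1 − π)d², where π is prevalence and d the outcome gap. The interval narrows by 1 − √(W/T). With an overall rate of 0.55 (assumed), T = 0.2475.
- π = 0.20, d = 0.30: W = 0.2331, 3% narrower.
- π = 0.20, d = 0.60: W = 0.1899, 12% narrower.
- π = 0.50, d = 0.30: W = 0.2250, 5% narrower.
- π = 0.50, d = 0.60: W = 0.1575, 20% narrower.

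A simulation of the Mantel-Haenszel against the crude risk difference (15,000 runs per setting, 32 and 40 per arm) gave standard deviations 2% to 20% smaller.

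**5. Small stratum.** At 20% prevalence, 16 of 80 is 8 per arm. With 64 women followed, 13 is about 6.5 per arm, with a 6% chance that one arm has 3 or fewer.

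**6. The categories, read literally.**
- A woman with a filled prescription but no viral load test in the past year meets the first care-status definition (one indicator is absent) and the second (one is present).
- Both categories begin from being linked to care. The inclusion criteria in section 10 require only living with HIV, so a never-linked woman fits neither.
- A woman abused by both a partner and a non-partner fits both perpetrator types. No rule is given.

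**The case against.** The strongest reply is that *groups* means sample composition. The sentence sits under Study Population, straight after eligibility, and names a sampling method; Aim 1 uses the same perpetrator split for composition. On that reading the imbalance figures do not bear on the sentence, and what remains is a missing count. Against this, section 10 moves on to the 40/40 randomization two sentences later, and the SAP uses *group* for arm. The documents do not settle it, so neither reading should be assumed.

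It is also fair to say that unstratified randomization of 80 women is legitimate in a descriptive pilot that claims no significance, and that the SAP already shows HIV care responses by arm at baseline. Both points stand. The second makes a care imbalance visible but does not account for it, and it does not mention perpetrator type.

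Four stronger inferences are tempting and unsupported:
- *Allocation was unstratified.* No strata are described; that does not show that none were used.
- *The comparison is biased.* Randomization is valid on average, and any imbalance would be chance.
- *Care status plainly means none versus any of the three indicators.* That may be the intent, but the literal wording overlaps and the documents do not choose.
- *The background retention rate tells us how many women will be out of care.* Its definition is not given, it may not match the trial's categories, and purposive sampling would override it.

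**Conclusion.** The point holds as a minor one. No mechanism stated in the documents delivers balance between arms, Aim 2 gives no counts against which to check composition, and the classification rules are not mutually exclusive or complete. If the arm reading applies and allocation was unstratified, the expected gap on one factor is about 7 to 9 points, with a 16% to 26% chance of 15 points or more. The mean gap would move a crude arm difference by about 2 to 5 points, against a 95% half-width of 22 to 24 points. These sizes rest on assumed prevalences of 20% to 50% and assumed outcome gaps of 30 to 60 points.

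The one analytic gap is that no estimate accounts for a baseline factor the plan itself singles out for balance.

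**What to change.** **Wording.** Say whether *groups* means arms or sample composition, and replace *ensure* with what was done: the strata if allocation was stratified, otherwise the recruitment target per category. Targets need care status at screening, and the screener items listed in section 9 do not name it, so say where it is obtained. Have the sponsor choose mutually exclusive research categories for care status and perpetrator type, with a place for never-linked women and for women reporting both types.

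**If allocation is still open.** Stratify permuted blocks by care status from the baseline survey, which is completed before assignment is disclosed. With blocks of 4 (illustrative), an incomplete last block leaves the arms at most 2 women apart in each of two strata, so the gap on care status is at most 2/40 = 5 points.

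**If it is closed, as the past-tense SAP suggests.** Tabulate both factors by arm. Add, labelled post hoc and as estimates rather than tests, Mantel-Haenszel risk differences with 95% confidence intervals, stratified by baseline care status, for retention and viral suppression. Give an analogous baseline-adjusted estimate for hair-measured ART adherence. First, the sponsor must confirm that the survey or the medical records hold the three past-year indicators: the survey outline does not name them, and the chart abstraction lists visits, viral load and CD4 but not prescriptions.

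**Cost.** A few sentences, one table and three estimates, or one stratified list. The gain is modest (intervals about 3% to 20% narrower under the assumed gaps), a small out-of-care stratum would be imprecise, and intervals would be added to a plan that is otherwise descriptive.

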### **Study Screening and Enrollment:**

#### **AIM 1**

In Phase 1 (Aim 1), three separate recruitment strategies will be imposed based on the distinct types of focus groups, key informant interviews, and beta testing.

- Black WLHA with a history of interpersonal violence (n=6-8 per FG; total of 4 FGs and n=8 Beta Testing) will be recruited from organizations in San Diego, CA that provide HIV testing and/or treatment to WLHA, all of which are represented through membership in the San Diego CFAR Disparities Core CAB. We will also recruit Black WLHA through presentations at organizations providing HIV-related services such as Mental Health America San Diego and the Center for Community Solutions Rape Crisis Center. Finally, we will distribute flyers and advertisements through street outreach efforts, community events, and newspapers such as the Voice and Viewpoint, an African American local newspaper. We have successfully utilized these recruitment efforts in previous studies. Interested women be screened over the phone. They will provide verbal consent to be screened, then asked questions regarding eligibility, demographics, and computer literacy.
- Peer Navigators (n=4-6; one FG) will be identified by [name] contact with leadership at local clinics and CBOs known to employ peer navigation approaches and represented on the CAB (e.g., UCSD Mother, Child and Adolescent HIV Program and San Ysidro Health Center). Invitations will be extended to each organization with a flyer to be provided to PNs.
- Key Informants (n=4-6) will be identified by [name] in-person or phone contact with leadership at local clinics and community-based organizations known to provide services to women in the areas of

HIV/AIDS care and domestic violence services such as UCSD Owen Clinic and Mental Health America. Print and electronic promotional materials will include a brief description of the study and the study phone number to call for more information about the study.

For all focus groups, interviews, and beta testing, participants will be asked to provide [name] and [name] with contact information. Focus group and interviews will be scheduled for dates and time convenient for the participants. All participants will review informed consent documentation and provide informed consent prior to commencement of the focus groups or interviews.

## **AIM 2**

In Phase 2 (Aim 2), we will conduct the pilot RCT with 80 women from the study population. Potential participants will be recruited through community contacts across San Diego County, Los Angeles County, Alameda County, Oklahoma City County, and Tulsa County. Members of the research team have established relationships with the following key organizations that provide HIV testing and/or treatment to WLHA and these organizations are represented through membership in the San Diego CFAR Disparities Core CAB: UCSD Owen Clinic, UCSD Mother, Child and Adolescent HIV Program, Family Health Centers of San Diego, San Ysidro Health Center. We will also extend recruitment to Black WLHA through presentations at organizations providing HIV-related services such as Mental Health America San Diego, Neighborhood House Association, and the Center for Community Solutions Rape Crisis Center. In Los Angeles County, we will recruit from the following community-based organizations: UCLA Family AIDS Network, AIDS Project Los Angeles, Maternal Child Adolescent Clinic, OASIS Clinic, East LA Women's Center, Alta Med, and JWCH Institute. In Alameda County, we will recruit from WORLD, an HIV service organization for women of color. In Oklahoma City and Tulsa Counties, we will recruit from Guiding Right, Inc., a Black-focused community-based organization. In all counties, we will distribute flyers and advertisements through street outreach efforts, community events, and newspapers such as the Voice and Viewpoint, an African American locally based newspaper. Finally, we will employ Facebook Advertising to recruit women through social media, including on the platforms Facebook and Instagram, and using the Facebook Audience Network to run advertisements on other websites the target population is likely to utilize. We have successfully utilized these recruitment efforts in previous studies. Further, we will employ Build Clinical, an organization that assists academic researchers in study enrollment through technology and novel data-driven approaches.

Depending on the recruitment source, the following initial contact method may be employed: (1) Women may see the study advertisements in the community. Women interested in participating in the study will contact the study staff using the study phone number and email address listed in order to receive study information. At the time of the initial contact, women will be provided information regarding LinkPositively. Women will then express whether or not they are interested in the study. (2) Women may be recruited via service agencies or enrolled participants. By reviewing the study advertisement, interested women may request that their contact information be provided to the study team in order to initiate the first contact. At the time of the initial contact, women will be provided information regarding LinkPositively. Women will then express whether or not they are interested in the study. (3) Women may see the study advertisement on social media. By following the link on a social media advertisement, women can review the study website and complete the screener online (see below) and provide contact information for the Project Coordinator to directly contact them. At the time of the initial contact, women will be provided information regarding LinkPositively. Women will then express whether or not they are interested in the study.

Depending on the preference of the potential participant, the following screening method may be employed: (1) If a potential participant would like to be screened by phone for eligibility, the study staff will seek verbal consent to screen the participant. If consent is obtained, then a 10-minute screener will be conducted to assess eligibility. Screening questions will include age, biological sex, preferred gender identity, pregnancy status, HIV status, and sexual and reproductive history. (2) If a potential participant would like to be screened digitally for eligibility, the potential participant can follow a link on the advertisement, the study website, or via a link sent to them directly by the study staff. This link will take them to an eligibility screener via REDCap survey

or to a secure survey via Build Clinical. The survey link will first notify potential participants that by continuing to the study screener, they are providing consent to be screened digitally. If consent is obtained, then a 10-minute screener will be conducted to assess eligibility. Screening questions will include age, biological sex, gender identity, self-reported HIV status, and measures pertaining to lifetime trauma, mental health, post-traumatic stress, past year physical and/or sexual violence, and substance and alcohol use. Due to the highly sensitive nature of this study, ability of potential participants to screen digitally will reduce participant burden in the screening process and increase participant options in the screening process, as is aligned with a trauma-informed approach to working with WLHA.

After eligibility is determined, eligible participants who screened through REDCap will be asked to provide the study staff with their contact information (phone number, email address), along with the names and corresponding contact information (e.g. phone number) of up to 3 individuals who may be contacted if the research team is unable to contact the participants for study initial visits and/or follow-up visits. The research team will only contact these alternative contacts if we cannot reach the participants through 10 attempts (total) on different days and times using the contact details that the participants provided the research team. Eligible participants who are recruited through Build Clinical will provide contact information through the secure participant management platform, which is kept secure using server authentication and data encryptions that are the same as those used in healthcare institutions. Data is transmitted via HTTPS, and Build Clinical uses a Transport Layer Security (TLS) 1.2 with a 2048-bit server key lengths and industry-leading modern browsers. No subject data other than eligibility screening data is stored by Build Clinical. All servers are based in the US, and data will be deleted upon request from the UCSD research upon closing of the study. The screening survey used through Build Clinical is identical to that used in REDCap.

Participants deemed eligible for the study will then be linked to the Project Coordinator to schedule a baseline study visit at the UCSD Antiviral Research Center in San Diego County, the Charles R. Drew University Clinical and Translational Science Institute in Los Angeles County, WORLD in Alameda County, and at Guiding Right, Inc. offices in Oklahoma City and Tulsa Counties. At the baseline visit, participants will review and sign informed consent documentation to be enrolled in the study.

